2. STUDY DESIGN

This study is a Phase 2, multicenter, randomized, double-masked, vehicle-controlled, parallel-group clinical trial. The investigator and his/her staff will not know which study medication the subject is receiving but will be able to determine this in the event of an emergency.

Prior to enrollment, the study will be discussed with prospective subjects and those wishing to enter will be asked to give written informed consent. Informed consent will be obtained prior to any study related procedures being performed. Once informed consent has been obtained, the subjects will be questioned regarding their medical history to determine whether or not they are in satisfactory health to enter the study and to determine if they meet the specific entry criteria.

During the screening phase (Day -2 to Day -14) of the study, subjects who meet all inclusion and none of the exclusion criteria will be randomized in a 1:1 ratio: 40 subjects in the 0.2% BSP group and 40 subjects in the vehicle group.

During the dosing phase (Day -1 to Day 14), subjects will dose BID for 16 days: the day before cataract surgery, the day of cataract surgery, and for 14 days after cataract surgery. Subjects will then be followed for approximately 2 weeks during the evaluation phase (Day 15 to Day 32).

There will be 7 study visits for full study participation: 1 visit during the screening phase, 3 visits (Day 0, Day 1 and Day 8) during the dosing phase, and 3 visits (Day 15, Day 22, and Day 32) during the evaluation phase.

Subjects will instill 3 doses of study drug prior to surgery (2 doses on Day -1, and 1 dose on Day 0 prior to surgery), 1 dose in the evening after surgery and continue dosing BID for 14 days after surgery.

Subject safety will be evaluated throughout the study. The safety parameters to be assessed are the incidence of adverse events (AEs) and serious adverse events (SAEs), discontinuations due to AEs, changes in visual acuity (VA) and intraocular pressure (IOP), and biomicroscopic and ophthalmoscopic findings.

Efficacy will be assessed by biomicroscopic measurement of anterior chamber cells (ACCs) and measurement of the subject's pain level at each visit using a visual analog scale (VAS). Subject pain will also be assessed by subjects at home using a subject diary.

All ratings and procedures should be performed by the same examiner from visit to visit whenever possible.

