10. STATISTICAL ANALYSES

10.1. Randomization, Stratification, and Masking

Eligible subjects will be randomly assigned to each of treatment groups in a 1:1 ratio according to a validated SAS® computer-generated central randomization schedule. The randomization schedule contains the coded treatment assignments for each randomization number. The

randomization plan will be based on the study design, number of treatment groups and number of sites.

The randomization is generated by an un-masked statistician who is not affiliated with the study. The randomization plan is shared with the Sponsor's designee responsible for final clinical packaging and labeling to allow for proper packaging and labeling of the study drug supply. Access to the randomization code will be strictly controlled according to the Sponsor designee's Standard Operating Procedures (SOPs).

The randomization is not unmasked until the study is complete and the database is locked. The Sponsor will confirm in writing that there are no regulatory or quality issues which preclude the unmasking of the study.

Unmasking of the randomization code prior to study completion due to a medical emergency will be managed in accordance with the Sponsor designee's SOP. All unmasked cases will be fully documented. Otherwise, the study mask will remain intact.

In this double-masked study, the investigator and his/her study staff, the subject (including caregiver, if applicable) and Sponsor/designee (other than as stated above) are masked to the identity of the study drug.

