10.2. Efficacy and Safety Variables

Primary Efficacy Endpoint(s): The primary efficacy endpoint will be the proportion of subjects with ACC grade of 0 (cell count=0) at Day 15. Subjects with an ACC grade of >0 at Day 15 or who receive rescue medication prior to Day 15 will be treated as failures. Last-observation-carried-forward (LOCF) will be used for the intent-to-treat (ITT) analysis.

Secondary Efficacy Endpoint: The secondary efficacy endpoint is the proportion of subjects who achieve a pain score of 0 at each post-surgical VAS (0-100 millimeter [mm] scale) assessment (Days 1, 8, 15, 22 and 32).

Safety Variables: AEs, BCVA, IOP, biomicroscopic and ophthalmoscopic findings.

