10.6. Efficacy

10.6.1. Primary Efficacy Analysis

The primary efficacy analysis will test for a difference in the proportion of subjects with ACC grade zero (0) in the SURF-201 active treatment group versus the vehicle group only at Day 15. An ACC grade of zero is considered to be a success, and an ACC grade >0 or the use of rescue medication prior to Day 15 is counted as a failure (as described in Section 3.1). Missing data will be imputed using LOCF in the ITT population only.

The test will be the z-test for proportions and will be reported with associated z-based 95% confidence interval (CI). The null hypothesis is that the proportions are equal, and this will be a two-sided test at the alpha = 5% level. If the assumptions of the z-test are not satisfied, a Barnard's exact test and exact 95% CIs will be presented.

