10.6.2. Secondary Efficacy Analysis

The differences in the proportion of subjects who achieve a pain score of 0 on the VAS at each post-surgical assessment between SURF-201 and vehicle will be tested using a z-test for proportions with a 95% CI. The null hypothesis is that the proportions are equal, and this will be a two-sided test at the alpha = 5% level. If the assumptions of the z-test are not satisfied, a Barnard's exact test and exact 95% CIs will be presented.

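### Does leaving the z-test's switching rule, variance form and exact interval method unstated put the primary conclusion at risk?

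*Combined protocol and SAP*

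**What the plan says.** Section 10.6.1 names one test for the primary endpoint: "The test will be the z-test for proportions and will be reported with associated z-based 95% confidence interval (CI"). The null hypothesis is equal proportions, and "this will be a two-sided test at the alpha = 5% level". The fallback is conditional. "If the assumptions of the z-test are not satisfied", Barnard's "exact test and exact 95% CIs will be presented".

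Section 10.6.2 treats the secondary pain endpoint in the same way. The differences "will be tested using a z-test for proportions with a 95% CI", with the same fallback. Section 10.2 lists five occasions for it: each post-surgical VAS "assessment (Days 1, 8, 15, 22 and 32").

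The planned size, in Section 2, is "40 subjects in the 0.2% BSP group and 40 subjects in the vehicle group". Section 10.1 adds that "The randomization is not unmasked until the study is complete and the database is locked".

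No section gives a cell-count criterion, says whether the variance is pooled, mentions a continuity correction, or names the exact interval. Section 10.5 adds only the software and the two-sided 5% level.

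**The concern.** A reader who tries to program the analysis from Section 10.6.1 meets four open choices:

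1. When the z-test's assumptions count as failed. Textbook rules use observed or expected cells, with a minimum of 5 or 10.
2. Whether the exact result replaces the z-test or stands beside it.
3. Whether the z statistic and its interval use pooled or unpooled variance, with or without continuity correction.
4. Which exact interval is meant. One built by ordering on the raw difference can include zero when Barnard's test rejects.

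If these choices were settled after the treatment code was opened, a result near 5% could be reported either way. The same wording covers five pain visits, so the visits might also be tested by different methods. At stake would be the credibility of a borderline primary result.

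**Working it through.** **Inputs.** 40 per arm (Section 2); two-sided 5% (Sections 10.5 and 10.6.1); binary endpoint (Section 10.2). The documents give no success rates and no power figure, so there is no stated figure to reproduce. Assumed rates, active v vehicle: 50% v 20%, 40% v 15%, 30% v 10% and 55% v 30%. The four count rules are also assumptions: smallest observed cell, or smallest expected cell, at least 5 or at least 10. All 41 × 41 = 1,681 outcome tables were enumerated with exact binomial probabilities.

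**Formulas.** For x₁ and x₂ successes in 40, p̂ = (x₁ + x₂)/80.
- Pooled: z = (x₁ − x₂)/40 ÷ √[p̂(1 − p̂) × 2/40].
- Unpooled: the same numerator, over √{[p₁(1 − p₁) + p₂(1 − p₂)]/40}.
- Barnard: the probability of all tables with |z| at least as large, maximised over the common success rate.

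**Switching rule.**
- 11 v 4: difference 0.175, p̂ = 0.1875, SE = √(0.1875 × 0.8125 × 0.05) = 0.0873, z = 2.005, p = 0.045. Barnard p = 0.057. The smallest expected cell is 7.5 and the smallest observed is 4. Only the expected-at-least-5 rule keeps the z-test.
- 15 v 7: difference 0.200, p̂ = 0.275, SE = 0.0998, z = 2.003, p = 0.045. Barnard p = 0.057. Only the observed-at-least-10 rule leaves the z-test.
- The mirror images, 36 v 29 and 33 v 25, behave the same way.

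These are the only four tables favouring active on which the choice of rule changes the conclusion.

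| Assumed rates | Any two of the four rules pick different tests | Same, without observed ≥10 | Choice of rule changes the conclusion |
|---|---|---|---|
| 50 v 20 | 73% | 8% | 0.6% |
| 40 v 15 | 93% | 38% | 2.3% |
| 30 v 10 | 97% | 86% | 3.2% |
| 55 v 30 | 20% | 0.3% | 0.03% |

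The second column looks alarming, but picking a different test is rarely reaching a different conclusion. The last column is the one that matters.

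**Direction of the discordance.** On 10 tables favouring active the pooled z-test rejects and Barnard's does not. On none is it the other way round. Maximum size over the common rate is 5.9% for the pooled z-test and 4.8% for Barnard's. The pooled z-test runs at 5.1%, 4.8% and 5.2% for common rates of 20%, 30% and 40%.

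**Variance form.** At 16 v 8, pooled SE = √(0.3 × 0.7 × 0.05) = 0.1025, z = 1.952, p = 0.051. Unpooled SE = √[(0.24 + 0.16)/40] = 0.100, z = 2.00, p = 0.046, with interval 0.200 ± 0.196 = 0.004 to 0.396. Only this table and 32 v 24 are affected, with combined probability 0.9%, 1.4%, 0.1% and 0.1% in the four scenarios. With equal arms the unpooled variance never exceeds the pooled one, so the unpooled z-test is the most liberal of the three candidates. Its maximum size is also 5.9%. An analyst who chose the most favourable of the three after seeing the data would therefore still not exceed 5.9%.

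**Continuity correction.** It would reverse 40 tables favouring active (14 v 6: p = 0.039 without, 0.071 with) and lower power from 81.7% to 74.9% at 50 v 20. Its maximum size is 3.3%.

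**Exact interval.** At 12 v 4 Barnard p = 0.033. The exact lower limit is −3.1 points when ordered on the raw difference and +1.9 when ordered on the score statistic. At 40 v 15, the probability of using Barnard's test and meeting this conflict is 3.1% (observed ≥5), 0.01% (expected ≥5), 14.2% (observed ≥10) or 6.3% (expected ≥10). At 50 v 20 it is 4.6% under observed ≥10 and at most 0.4% under the others.

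**Gain from writing a rule.** Take the z-test if pooled successes and pooled failures are each at least 10 (expected cells of at least 5 with equal arms), and Barnard's test otherwise. Maximum size is then 5.7%, against 5.9% for the z-test alone. Power differs by at most 0.1 point: 63.1% v 63.2% at 30 v 10, and no difference to that accuracy in the other three scenarios.

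**The case for a change.** The strongest case for a change is that the omissions are genuine, cheap to repair, and bear on the single primary test. A continuity correction alone would decide the result in 6.7% to 13.8% of trials across the four scenarios. A raw-difference exact interval could contradict the p-value printed beside it. The masking statement in Section 10.1 does not require the options to be fixed before the code is opened.

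Part of this stands. The text is silent on the threshold and on the exact interval, and nothing obliges the team to settle them before unmasking. The rest is weaker:

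- **Continuity correction.** The plan never mentions one. A z-test for proportions, paired with a z-based interval, ordinarily means the uncorrected test. The large power figures describe a departure from the plan.
- **Which result decides.** A fallback that applies only when a test's assumptions fail replaces that test. Reading it as a second, competing result is strained.
- **Interval conflict.** It requires the analyst to pick an ordering that the plan does not name and that does not match the test. The 14% figure also needs the strictest of the four count rules.
- **Different tests at different visits.** An assumption-based fallback is meant to do this when success rates change from Day 1 to Day 32. A written count rule applied visit by visit would do the same.
- **Late choice.** Expected cells under the null need only the pooled success count and the arm sizes, so the check can be made without the treatment code.

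**Conclusion.** No change follows. This is missing detail that an experienced analyst fills sensibly: an uncorrected z-test, with Barnard's test in its place when counts are sparse. The endpoint, time point, null hypothesis, level, sidedness, main test and named fallback are all fixed in advance.

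On that reading the unstated threshold changes the conclusion in about 0.03% to 3.2% of trials, on four borderline tables favouring active. The variance form matters on two. The switch cannot raise the type I error above that of the z-test already chosen. That test's maximum of 5.9% is a modest excess in a Phase 2 trial of this size. Using Barnard's test throughout would hold 5%, but it costs 0.7 points of power at 50 v 20 and 3.3 at 30 v 10, which is a trade-off for the sponsor and not a correction.

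These figures assume 40 analysed subjects in each arm, the stated success rates and the four illustrative count rules. The ITT population may be smaller or unequal. At 38 per arm the rule-dependent tables rise from four to eight, which is still a small set of near-threshold results.

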10.6.2. Secondary Efficacy Analysis

The differences in the proportion of subjects who achieve a pain score of 0 on the VAS at each post-surgical assessment between SURF-201 and vehicle will be tested using a z-test for proportions with a 95% CI. The null hypothesis is that the proportions are equal, and this will be a two-sided test at the alpha = 5% level. If the assumptions of the z-test are not satisfied, a Barnard's exact test and exact 95% CIs will be presented.

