10.5. Statistical Methods: General Principles

All data processing, summarization and analyses will be performed using Sponsor designee’s SAS Environment / Version 9.4 (or later) of the SAS® statistical software package. The principles that will be applied to all tables, listings and figures (TLFs) unless otherwise stated are outlined in Table 1.

Table 1: Principles for All TLFs

Principle	Value
Baseline	Defined as the last measurement taken prior to dosing (Day -14 to Day -2).
Significant tests	Two-sided and use a 5% significance level for main effects and 10% significance level for interaction terms.
Treatment group labels and order presented	SURF-201 Vehicle
Tables	Data in summary tables presented by treatment group, assessment and visit (where applicable).
Listings	All data collected presented by treatment group, site, subject number, and visit (where applicable), unless otherwise specified.
Descriptive summary statistics for continuous variables	Number of subjects/observations (N), mean, standard deviation (SD), median, minimum (min) and maximum (max).
Descriptive summary statistics for categorical variables	Frequency counts and percentages [n (%)]
Denominator for percentages	Number of subjects in the analysis population, unless stated otherwise
Include “Missing” as category	No, N will change, unless stated otherwise
Display for 0 percentages	-
Display to one more decimal place than collected value	Mean Standard Error Mean Difference Median
Display to two more decimal places than collected value	Standard Deviation Confidence Interval
Date Format	DD-MMM-YYYY

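### Does testing the one secondary pain endpoint at five visits, each at 5%, need a deciding visit or a multiplicity rule?

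*Combined protocol and SAP*

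**What the plan says.** Section 10.2 defines a single secondary endpoint, "The secondary efficacy endpoint is the proportion of subjects who achieve a pain score of 0 at each post-surgical VAS", and then lists the visits: "assessment (Days 1, 8, 15, 22 and 32". Section 10.6.2 analyses "The differences in the proportion of subjects who achieve a pain score of 0 on the VAS at each post-surgical assessment" by a z-test for proportions with a 95% confidence interval, and falls back on Barnard's exact test. It gives the level as "this will be a two-sided test at the alpha = 5% level". Table 1 in Section 10.5 sets the same general rule, "Two-sided and use a 5% significance level for main effects", and has summary tables broken down by visit as well as by treatment group.

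The primary analysis in Section 10.6.1 is tied to one visit; it compares the proportion with no anterior chamber cells "in the SURF-201 active treatment group versus the vehicle group only at Day 15". Section 2 describes the trial: "This study is a Phase 2, multicenter, randomized, double-masked, vehicle-controlled, parallel-group clinical trial", with 40 subjects per arm. Section 10.1 adds that "The randomization is not unmasked until the study is complete and the database is locked".

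No section names a deciding visit for pain, sets an order of testing, adjusts the level, makes the pain tests conditional on the primary, or calls them nominal or exploratory.

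**The concern.** One endpoint yields five p-values, each judged at 5%, and no rule says when the endpoint has been met. The authors fixed the primary to a single visit and then did not do so for pain in the very next section, which makes the omission look like an oversight. If Day 8 favoured SURF-201 and Day 15 did not, the plan would not say whether the pain endpoint succeeded, and that judgement could be made after unmasking. Someone who counted any significant visit as success would face a false-positive risk well above the nominal level, and a chance result could be reported as a pain effect.

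**Working it through.** **Inputs.** Five visits (Section 10.2), a two-sided level of 0.05 per test (Section 10.6.2 and Table 1), and 40 per arm (Section 2). The correlation between visits and the pain-free rates are not in the documents, so both are assumptions here.

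**Which analysis is meant.** The word "each" in Section 10.2 might suggest one responder endpoint: pain-free at all five visits. Section 10.6.2 speaks of differences in the plural at each assessment, Section 10.2 lists the days separately, and Table 1 presents results by visit. Together these point to visit-by-visit tests. The responder reading would in any case give one test and no multiplicity.

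**The plan's own figure.** The 5% is the level of each visit's test. The plan states no error rate for the five visits together, so there is no joint figure to reproduce or contradict.

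**Error rate if any one visit counts as success, with all five nulls true.**

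- Independent visits, either direction: 1 − 0.95^5 = 1 − 0.774 = 0.226.
- Independent visits, favouring SURF-201: 1 − 0.975^5 = 1 − 0.881 = 0.119.
- Upper bound, either direction, whatever the dependence: 5 × 0.05 = 0.25.

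With correlated z-statistics (simulation of five normal statistics, 2,000,000 draws per setting; the lower figure is equal correlation between all visits, the higher is first-order autoregressive):

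| Correlation | Either direction | Favouring SURF-201 |
|---|---|---|
| 0.5 | 0.183–0.201 | 0.092–0.102 |
| 0.7 | 0.148–0.172 | 0.074–0.086 |
| 0.9 | 0.102–0.118 | 0.051–0.059 |
| 1.0 | 0.050 | 0.025 |

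A check with binary data was also run: 40 per arm, pooled z-test, and assumed pain-free rates rising from 30% to 70% or from 40% to 80%. A latent correlation of 0.9 between visits gave a mean z-statistic correlation of only 0.55–0.60. The error rate was 0.167–0.178 in either direction and 0.085–0.088 favouring SURF-201. So if the any-visit rule applied, the middle and upper parts of the range would be the more realistic.

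**Error rate under other rules.** If all five visits had to be significant, the rate in either direction would be 0.009–0.017 at correlation 0.9 and never above 0.05. If one visit were named in advance, it would be 0.05. The inflation therefore comes from the any-visit rule, not from running five tests.

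**What a formal rule would cost.** Power is Φ[(d − 1.96·s0)/s1], where d is the difference in proportions, and s0 and s1 are the pooled and unpooled standard errors with 40 per arm.

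- A deciding visit with an assumed 70% v 40% pain-free: d = 0.30, s0 = √(2 × 0.55 × 0.45/40) = 0.1112, s1 = √((0.21 + 0.24)/40) = 0.1061. Power = Φ(0.773) = 0.780 (exact enumeration 0.796).
- A deciding visit where most are already pain-free, assumed 90% v 80%: d = 0.10, s0 = √(2 × 0.85 × 0.15/40) = 0.0798, s1 = √((0.09 + 0.16)/40) = 0.0791. Power = Φ(−0.715) = 0.237 (exact enumeration 0.247).
- Bonferroni, 0.05/5 = 0.01 per visit, with an assumed 60% v 30%: power falls from 0.780 to 0.550.

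**The case for a change.** The strongest case for a change is that the plan does not present the pain tests as supportive. It states a null hypothesis and a level in the same terms as for the primary, and pain is one of only two efficacy measures in the design. With the code masked until database lock, a rule written beforehand would be credible, and one written afterwards could be challenged. The cost is a sentence or two, with no added subjects or visits.

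What stands is that no rule for reading the five results together is written down, and that if any single visit were taken as success the error rate would rise as shown. What does not stand is the step from there to a defect in the analysis. The documents make no formal pain claim and set no success criterion that the tests could breach. The visits, method and level are all fixed in advance and nothing permits leaving a visit out, so a reader will see all five results with their intervals and can judge an isolated significant visit accordingly. The lightest remedy, calling the tests nominal, alters no test, estimate or interval. The heavier ones, a deciding visit or a fixed order, are real choices on which statisticians would differ, because power depends heavily on the visit chosen.

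**Conclusion.** No change follows. The missing piece is a rule of interpretation, which analysts of a Phase 2 trial ordinarily supply by reading unadjusted secondary tests as supportive. Each pain test keeps its stated nominal 5% level, and the primary's error rate is unaffected.

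The size of the concern is conditional. Only if any one significant visit counted as success, and there were no true effect at any visit, would the false-positive chance be about 5–12% favouring SURF-201 (2.5% for a single visit) or about 10–23% in either direction (5%), for an assumed between-visit correlation of 0.9 down to 0. The conclusion rests on the visit-by-visit reading of Section 10.6.2, on all five results being reported as planned, and on no formal efficacy claim being built on a single pain visit. If such a claim were intended, the question would need to be reopened before unmasking.
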